14	Endpoints	24
15	Data collection	24
16	Randomization	25
17	Statistical considerations	25
	17.1 Sample size and power considerations	25
	17.2 Statistical analysis.....	26
	17.2.1 Efficacy analysis	26
	17.2.2 Toxicity analysis.....	27

17.2.3	Additional analyses	27
17.3	Data and safety monitoring board.....	27
17.4	Interim analyses and safety monitoring	27
18	Ethics	28
18.1	Independent ethics committee or Institutional review board.....	28
18.2	Ethical conduct of the study.....	28
18.3	Patient information and consent	28
19	Trial insurance	28
20	Publication policy	29
21	Glossary of abbreviations.....	30
22	References.....	32

APPENDICES

A	Diagnostic criteria Chronic Myeloid Leukemia.....	34
B	CML risk assessment	35
C	Response criteria for Chronic Myeloid Leukemia	37
D	Toxicity criteria	40
E	ZUBROD-ECOG-WHO Performance Status Scale	41
F	NYHA* scoring list	42

3 Synopsis

Study phase	Phase III
Study objectives	To determine the efficacy of the combination of imatinib with cytarabine as compared to imatinib alone in terms of the rate of molecular response at 12 months from randomization.
Patient population	Patients with Chronic Myeloid Leukemia, Philadelphia-positive (cytogenetics) or bcr-abl positive (PCR), in first chronic phase \leq 2 months from diagnosis, age 18-65 years inclusive
Study design	Prospective, multicenter, randomized
Duration of treatment	Until progression
Number of patients	330 patients registered and randomized
Adverse events	Adverse events will be documented if observed, mentioned during open questioning, or when spontaneously reported
Planned start of recruitment	I 2006
Planned end of recruitment	I 2011

4 Investigators and study administrative structure

Responsibility	Name	Affiliation/Address
Study Coordinators	[name]	Erasmus MC, Rotterdam
	[name]	VUMC, Amsterdam
	[name]	UZ Gasthuisberg, Leuven
Writing Committee	[name]	UMC St. Radboud, Nijmegen
	[name]	LUMC, Leiden
	[name]	UMCU, Utrecht
	[name]	AMC, Amsterdam
	[name]	VUMC, Amsterdam
	[name]	Medisch Spectrum Twente, Enschede
	[name]	Erasmus MC, Rotterdam
	[name]	UMCG, Groningen
	[name]	Haga Ziekenhuis, Den Haag
	[name]	Meander MC, Amersfoort
	[name]	Isala Klinieken, Zwolle
	[name]	AZM, Maastricht
	[name]	Atrium MC, Heerlen
	[name]	Albert Schweitzer Ziekenhuis, Dordrecht
	[name]	UZ Gasthuisberg, Leuven
Network Molecular Diagnostics	[name],	Erasmus MC, Rotterdam
	[name]	
Statistician	[name]	HOVON Data Center, Rotterdam
Datamanagement	[name]	HOVON Data Center, Rotterdam
Serious Adverse Events (SAEs) notification	HOVON Data Center	[contact]

5 Introduction

Chronic myeloid leukemia (CML) is a myeloproliferative disorder characterized by a reciprocal translocation between chromosome 9 and 22 (t(9;22)(q34;q11)) referred to as the Philadelphia chromosome. It results in the generation of a new oncogene (bcr-abl) encoding for a protein with constitutive tyrosine kinase activity causing a variety of cellular changes responsible for the malignant phenotype of CML (1). The disease is characterized by an initial indolent chronic phase usually followed after a median time of 4-5 years by a blastic transformation, highly resistant to further therapy. Classical treatment with hydroxyurea or busulphan does not alter the clinical course while interferon with or without cytarabine (Ara-C) can induce, mostly temporarily, cytogenetic responses in a minority of the patients resulting in a survival advantage (2). Complete eradication of the malignant clone is currently only achieved by (non-)myeloablative chemo/radiotherapy followed by an allogeneic stem cell transplantation (3). However this procedure is only applicable for a limited number of patients and is still associated with considerable morbidity and mortality. The introduction

of imatinib mesylate (IM, Glivec[®]) has dramatically changed the treatment of CML patients. IM exerts its tyrosine kinase inhibiting action by stabilizing the inactive non ATP-binding conformation of BCR-ABL. In Phase I and II studies that included interferon unresponsive, accelerated and blastic phase patients, remarkable clinical responses were attained, with relatively minor side effects. Currently IM is appreciated as a first line drug in the treatment of CML, resulting in hematological (98%), major (91%) and complete (84%) cytogenetic responses in newly diagnosed patients as reported in the 42 months update of the IRIS study at ASH 2004 (3-5). Also, molecular responses are noticed: approximately 40% of the patients achieve a greater than 3-log reduction of the BCR-ABL protein, leading to a sharp decline in the chance of progression (5). Currently, the major aim of treatment is not only to achieve a cytogenetic response, but, preferably to attain a molecular response.

Resistance against IM can be caused by a variety of mechanisms, including overexpression of BCR-ABL, P-glycoprotein overexpression, the emergence of additional chromosomal abnormalities and, probably most important, the occurrence of point mutations in the ATP binding and kinase domains of the BCR-ABL protein leading to interference of the IM-BCR-ABL interaction (6). So, despite the high success rate of IM in terms of cytogenetic and molecular responses that translate in prolonged overall and disease-free survival, patients with unsatisfactory responses still pose a considerable problem. Successors of the tyrosine kinase inhibitors effective against cell lines transfected with a variety of point-mutated bcr-abl fusion genes are now finding their way into early clinical studies, thus hopefully tackling the problem of IM resistance (7,8). Dose escalation and/or combination with chemotherapy has already been investigated in phase II studies and phase III studies for the most promising approaches are currently being developed or have recently started.

5.1 Imatinib dose escalation

A clear dose-response relationship for IM has been shown in preclinical models. In the phase I studies no maximum tolerated dose (MTD) was observed, while here, a dose response relationship was already obvious. Of patients with cytogenetic resistance to the standard dose of IM of 400 mg/day, 34% responded to 800 mg/day, while in the accelerated phase of the disease escalation to 600 mg led to higher cytogenetic response rates and significantly better TTP and OS (9). In a phase II study from the MD Anderson Cancer Center, Houston, 114 patients with newly diagnosed chronic phase CML were treated with 800 mg IM (10). A major cytogenetic response was achieved in 109 patients (96%), including 103 (90%) with a complete cytogenetic response. With a median follow-up of 15 months, no patient has progressed to accelerated or blastic phase. The estimated 2-year survival rate was 94%. By quantitative polymerase chain reaction (QPCR) studies, 71 (63%) of 112 patients showed bcr-abl/abl percentage ratios decrease to less than 0.05%, and 31 (28%) to undetectable levels. Compared with standard-dose IM, high-dose IM was associated with significantly better complete cytogenetic responses ($P = .0005$), major molecular responses (QPCR $< 0.05\%$; $P = .00001$), and complete molecular responses (undetectable bcr-abl; $P = .001$). High-

dose IM was well tolerated but resulted in more frequent myelosuppression; 82% of patients continue to receive 600 mg or more of IM daily.

5.2 Dose escalation of imatinib in combination with cytarabine (HOVON 51 CML)

Cytarabine is an active drug in myeloid leukemia's, especially when intensified dosages are applied (11). In-vitro studies of IM and cytarabine showed synergistic anti-proliferative effects (12,13). With the aim to prevent resistance and to induce an early, high rate of molecular remissions, HOVON set out to evaluate the combination of IM and cytarabine in a dose-escalation study of consecutive cohorts treated with daily IM at dosages of 200 mg, 400 mg, 600 mg or 800 mg combined with intravenous cytarabine, added as 2 consecutive cycles of i.v. treatment at days 1-7 at a dose of 200 mg/m²/24 hrs or 1,000 mg/m²/24 hrs. Primary endpoints were dose-limiting-toxicity (DLT) and quantitative molecular response as assessed by standardized real-time QPCR of bcr-abl transcripts. Patients without a major molecular response after 12 months were evaluated for mutations by direct sequencing. From the start in August 2001 until September 2005, 159 pts have been included in cohorts I through V. According to pre-defined criteria, cohorts I-IV B were demonstrated feasible and accrual continues (cohort IV A) for evaluation of efficacy. At 12 months from the start of treatment, overall probabilities of developing a major ($\geq 3\log$ reduction of bcr-abl copies) or complete ($> 4.5\log$) molecular response were 56% (s.e. 5%) and 17% (4%), respectively. Overall survival was 91% (3%) at 24 months and progression-free survival was 85% (4%). Significantly higher molecular response rates were observed in patients treated with 600 mg or 800 mg imatinib, irrespective of dose of cytarabine. Conversely, the higher dose of cytarabine (1,000 versus 200 mg) appeared not significantly associated with an even better molecular response. With a median follow-up of 21 months, six patients developed accelerated phase and 1 patient developed a blastic crisis. Among 30 pts without a major molecular response at 12 months, 2 pts acquired a point mutation of the Abl kinase domain resulting in amino-acid substitutions Phe359Val and Glu459Lys, respectively. These results suggest that the combination of escalated IM combined with standard or intensified cytarabine may prevent resistance and mirrors the synergy of both drugs that was found in-vitro (14).

5.3 Rationale of the study

Both in-vitro and in-vivo studies have now suggested synergistic activity of imatinib and cytarabine. Especially, patients treated with 800 mg imatinib and cytarabine within the HOVON 51 CML study developed a major molecular response in 76% (s.e. 10%) and a complete molecular response in 41% (12%) within 12 months from treatment (see section 17). For comparison, 60% of patients treated with 800 mg imatinib only at the MD Anderson (10) developed a major molecular response and 25-30% a complete molecular response at 12 months, which suggests that cytarabine significantly adds to the efficacy of imatinib. The importance of a rapid major molecular response is underscored by the virtual absence of disease progression in such patients as reported by several investigators (15,16). Therefore, in order to answer the question whether the combination of high

dose imatinib combined with i.v. cytarabine may result in a higher rate of major molecular response and a lower incidence of disease progression as high dose imatinib alone, it is proposed to perform a prospective randomized phase III study in patients with first chronic phase CML. Following the completion of the HOVON 51 CML study in 2005, it is expected that accrual in the new randomized study will start early in 2006.

6 Study objective

To assess the efficacy of imatinib combined with i.v. cytarabine as compared to imatinib alone in terms of:

- ◆ The rate and duration of major molecular response
- ◆ The rate and duration of complete molecular response
- ◆ The rate and duration of complete cytogenetic response
- ◆ The rate and duration of complete hematological response
- ◆ Progression-free survival
- ◆ Overall survival
- ◆ Safety profile
- ◆ Actual dose-intensity delivered
- ◆ Incidence of mutations of abl-kinase domain

In addition, proteomic and genomic analyses are planned to identify potential biomarkers predictive of response and progression-free survival.

7 Study design

This is a prospective, open label, randomized phase III study. Details of all treatments (dose and schedule) are given in section 9.

7.1 Registration, randomization and study treatment

Patients with newly diagnosed CML, Philadelphia-positive or bc/abl positive, in first chronic phase meeting all eligibility criteria (see section 8.1) and having provided informed consent will be randomized between:

- Arm A: imatinib given orally at a total dose of 800 mg daily until progression
- Arm B: imatinib given orally at a total dose of 800 mg daily, combined with 2 successive cycles of i.v. cytarabine 200 mg/m², at day 1-7, in cycles I and II, followed by imatinib monotherapy (800 mg daily) until progression

Treatment according to study arms A or B will start following cessation of preceding therapy with hydroxyurea (HU) or cessation of preceding therapy with imatinib. Preceding therapy with HU is allowed for no longer than 2 months and preceding therapy with imatinib is allowed for no longer than 1 month.

8 Study population

8.1 Eligibility for registration

All eligible patients have to be registered and randomized before start of treatment (see section 16). Patients have to meet all of the criteria mentioned below.

8.1.1 Inclusion criteria

- ◆ Newly diagnosed patients with CML in first chronic phase ≤ 2 months;
- ◆ Presence of Philadelphia chromosome or bcr-abl rearrangement;
- ◆ Age 18-65 years inclusive;
- ◆ WHO performance status ≤ 2 (see appendix E);
- ◆ Written informed consent.

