11.2.6 Cytogenetic analysis

- ◆ Conventional cytogenetic analysis of at least 20 metaphases
- ◆ FISH analysis for Philadelphia chromosome (optional)

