17.2 Statistical analysis

All analyses will be according to the intention to treat principle.

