Hematological response

Complete hematological remission

Requires all of the following:

- ♦ Normalization of leukocyte count: $WBC < 10 \times 10^9/l$;
- ♦ Normal differentials without circulating immature forms; a percentage of circulating immature cells $\leq 2\%$ is compatible with complete hematological remission, provided that it concerns no immature forms other than myelocytes and metamyelocytes:
blasts = 0%, promyelocytes = 0%, myelocytes+metamyelocytes $\leq 2\%$;
- ♦ Normalization of platelet count: platelets $< 450 \times 10^9/l$;
- ♦ Disappearance of all clinical symptoms and signs of disease including palpable splenomegaly.

Partial hematological remission

Not fulfilling all the criteria for complete hematological remission, with $WBC \leq 20 \times 10^9/l$.

Failure

$WBC > 20 \times 10^9/l$, or progression of disease to accelerated phase or blastic crisis without prior complete hematological remission.

Cytogenetic response

At least 20 metaphases analysed by conventional cytogenetic analysis or 200 metaphases/interphases analysed by FISH.

Complete: Ph^+ chromosomes = 0%

Partial: Ph^+ chromosomes $> 0\%$ and Ph^+ chromosomes $< 35\%$

Minimal: Ph^+ chromosomes $\geq 35\%$ and Ph^+ chromosomes $< 100\%$

Absent: Ph^+ chromosomes = 100%

Patients with either complete or partial cytogenetic response are considered to have achieved a major cytogenetic response.

Molecular response

Complete response: ≥ 4.5 log decrease of bcr-abl mRNA detectable by real-time quantitative RT-PCR

Major Response: ≥ 3 log decrease of bcr-abl mRNA detectable by real-time quantitative RT-PCR

Partial Response: ≥ 1 log and < 3 log decrease of bcr-abl mRNA detectable by real-time quantitative RT-PCR

No response: < 1 log decrease of bcr-abl mRNA detectable by real-time quantitative RT-PCR

Molecular responses will be monitored by means of real-time quantitative RT-PCR for the bcr-abl fusion transcript. Protocols for real-time quantitative RT-PCR for bcr-abl will be standardized by the Dutch Network for Molecular Diagnostics. Quality control will also be performed under the supervision of the Dutch Network for Molecular Diagnostics.

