The real-time RT-PCR analyses will only be carried out in laboratories qualified according to the quality standards defined by the Dutch Network for Molecular Diagnostics. Samples from other hospital laboratories should be sent to one of the reference laboratories (for information please contact [name], Erasmus MC, Rotterdam, [contact]). The real-time quantitative RT-PCR results obtained in this study will be reviewed by the Dutch Network for Molecular Diagnostics. For patients in arm A real-time quantitative RT-PCR will be performed at entry, at 3, 6 and 12 months after entry and at 6 months intervals thereafter. For patients in arm B real-time quantitative RT-PCR will be performed at entry, after cycle I, after cycle II, at 6 and 12 months after entry and at 6 months intervals thereafter (Arm B).

Progression

Progression from complete hematological response

Requires any of the following after complete hematological response, confirmed by a second determination at least one month later:

- ♦ WBC $> 20 \times 10^9/l$ while under continuous imatinib treatment and in the absence of the use of steroids and/or growth factors;
- ♦ Appearance of blasts or promyelocytes in PB
- ♦ Myelocytes + metamyelocytes $> 5\%$ in PB
- ♦ Platelets $> 600 \times 10^9/l$
- ♦ Progressing splenomegaly to a size of > 5 cm below the mid left costal margin to be confirmed on two occasions at least 4 weeks apart

Progression without prior complete hematological response

A doubling of WBC confirmed by a second determination at least one month later with at least the second value $> 20 \times 10^9/l$.

Progression from major cytogenetic response

An increase in Ph⁺ cells in BM by at least 30 percentage points (e.g. from 20% to 50%, or from 30% to 60%) from the best achieved response and confirmed by a second cytogenetic analysis at least one month later.

Clonal evolution

The appearance of additional chromosomal abnormalities other than the Ph chromosome. Ph chromosome variants or complex Ph chromosome translocations are not considered to indicate disease acceleration.

D Toxicity criteria

The grading of toxicity and adverse events will be done using the NCI Common Terminology Criteria for Adverse Events, CTCAE version 3.0, published December 12, 2003. A complete document (72 pages) may be downloaded from the following sites:

<http://ctep.info.nih.gov/reporting/ctc.html>

<http://www.hovon.nl> (under Studies > Documents)

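### Patients without a Philadelphia chromosome are eligible, but complete cytogenetic response is 0% Ph-positive with no baseline condition, so they score as responders whatever the treatment does

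*Protocol*

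**What the plan says.** **Eligibility.** Section 8.1.1 asks for "Presence of Philadelphia chromosome or bcr-abl rearrangement". The synopsis gives the same two routes, by cytogenetics or by PCR, and section 7.1 repeats them. No exclusion in section 8.1.2 removes a patient who is bcr-abl-positive but Ph-negative.

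**Response.** Appendix C grades cytogenetic response by the percentage of Ph-positive chromosomes at the assessment. The top category reads "Complete: Ph^+ chromosomes = 0" per cent, and no starting value is required. Then: "Patients with either complete or partial cytogenetic response are considered to have achieved a major cytogenetic response". The assay rule is "At least 20 metaphases analysed by conventional cytogenetic analysis or 200 metaphases/interphases analysed by FISH". Section 11.2.6 lists FISH as optional and describes it as being for the Philadelphia chromosome.

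**Loss of response.** Progression from major cytogenetic response in Appendix C needs a confirmed rise in Ph-positive "cells in BM by at least 30 percentage points" from the best response achieved.

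**Use.** Section 14 makes the rate and duration of major and complete cytogenetic response a secondary endpoint, and section 17.2.1 adds time to complete cytogenetic response. Section 17.1 counts loss of cytogenetic response before 12 months as a failure on the primary endpoint. On the analysis population, section 17.2 says: "All analyses will be according to the intention to treat principle".

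**The concern.** The cytogenetic scale runs from 100% Ph-positive (absent response) to 0% (complete response). It assumes that every patient starts with Ph-positive metaphases, and the inclusion criterion does not require that. The other two response scales in Appendix C do not share the problem: hematological response requires normalisation, and molecular response requires a log decrease of bcr-abl mRNA.

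A patient with no Ph chromosome on karyotype therefore meets the top category before treatment and is credited with it at the first repeat marrow. This says nothing about imatinib or cytarabine. Such patients push up the complete and major cytogenetic response rates, add events to the time-to-response curve at times set by the visit schedule, and have a response duration that cytogenetic loss on karyotype cannot end. Each effect moves the two arms towards each other and makes the rates harder to compare with those of other trials.

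**Working it through.** **1. The plan's own figure.** The sample size concerns major molecular response (MMR), 60% versus 75%, with 80% power and two-sided α = 0.05 (section 17.1). Per arm, n = [1.96·√(2·0.675·0.325) + 0.8416·√(0.60·0.40 + 0.75·0.25)]² / 0.15² = 151.9, so 152 per arm and 304 in total. With the continuity correction, n/4·[1 + √(1 + 4/(n·0.15))]² = 164.9, so 165 per arm and 330 in total. The stated 330 is reproduced and is not affected by this point.

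**2. One patient followed through the rules.** The patient is bcr-abl-positive by PCR, has 20 or more analysable metaphases, and none is Ph-positive.
- Sections 7.1 and 8.1.1: eligible.
- Section 11.2: marrow cytogenetics at entry shows 0% Ph-positive. The next cytogenetic analysis is at month 3 (arm A) or after cycle II (arm B).
- Appendix C: 0% at that assessment is a complete, and so also a major, response.
- Appendix C, progression: by karyotype a 30-point rise in Ph-positive cells cannot occur.
- Section 17.2: nothing takes the patient out of the denominator.

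**3. Size.** Let q be the share of such patients, equal in expectation in both arms, and r the true response rate in the others. The observed rate is q + (1 − q)·r, and the observed arm difference is (1 − q) times the true one. The protocol gives no q, so 1% to 10% is assumed.

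At q = 5%:
- r = 30%, an assumed early rate: 0.05 + 0.95·0.30 = 33.5%.
- r = 84%, the complete response rate that section 5 cites for newly diagnosed patients on imatinib: 0.05 + 0.95·0.84 = 84.8%.

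For assumed true rates of 80% and 90% with 165 per arm, using the formula of step 1 without continuity correction:

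| q | Such patients among 330 | Observed rates | Difference (points) | Power |
|---|---|---|---|---|
| 0 | 0 | 80.0 v 90.0% | 10.0 | 72% |
| 1% | about 3 | 80.2 v 90.1% | 9.9 | 72% |
| 5% | about 17 | 81.0 v 90.5% | 9.5 | 70% |
| 10% | 33 | 82.0 v 91.0% | 9.0 | 67% |

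**4. What leaving them out does to power.** With 165·(1 − q) per arm and the undiluted 80% versus 90%, the same formula gives 70% at q = 5% (156.75 per arm) and 68% at q = 10% (148.5 per arm). Compared with the table, power hardly changes. The gain is an estimate that means what its name says.

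**5. Chance imbalance.** At q = 5% the between-arm difference in the share of such patients has SD √(2·0.05·0.95/165) = 2.4 points, and 1.96 SD is 4.7 points. Each extra such patient replaces one who would have responded with probability r, so the effect on the response difference is 4.7·(1 − r): 3.3 points at r = 30% and 0.8 points at r = 84%.

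**The case against.** **This belongs in the statistical analysis plan.** Who is evaluable for a secondary endpoint is often settled there, and the entry karyotype needed to settle it is collected. Intention to treat is also stated only as a principle, and it does not itself say that a patient with no Ph-positive cells at baseline is a responder. That is fair, but the scoring comes from Appendix C, which is the protocol's own definition and does not fit the protocol's own eligibility rule. The stated rule gives a wrong result, which is more than a detail left open.

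**FISH covers these patients.** Appendix C accepts FISH on interphases, and such a count could register positive cells in a karyotype-negative patient. This narrows the gap. It does not close it, because FISH is optional and nothing requires it, or a reading of bcr-abl fusion, in Ph-negative patients.

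**Randomisation deals with it.** Randomisation does prevent a systematic advantage for either arm in the response rates. It does not stop the inflation in both arms or the dilution.

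**No such patient may be enrolled.** The share is wholly assumed, and the protocol does not say how many are expected. This limits the size of the point, but the criterion was written to admit them.

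**Conclusion.** The point holds as a small defect in a secondary-endpoint definition. For q between 1% and 10%, an assumption, arm differences in complete or major cytogenetic response shrink by 1% to 10% of their size, and rates rise by q·(1 − r) in both arms.

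Four stronger readings are tempting, and the protocol does not support them:
- *These patients are responders from entry.* They meet the criterion at entry, but credit comes only at the first post-baseline cytogenetic assessment.
- *They can never progress.* Only cytogenetic loss by karyotype is closed to them. Hematological progression, accelerated phase, blastic crisis and clonal evolution remain open under section 10 and Appendix C.
- *A chance imbalance of 4.7 points passes straight into the response comparison.* It is multiplied by 1 − r (step 5), and it is ordinary sampling variation that the standard error already covers.
- *The primary comparison is compromised.* MMR is a log decrease of bcr-abl mRNA and does not depend on Ph status. The one link is the failure component for loss of cytogenetic response, which by karyotype cannot occur in these patients.

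**What to change.** Add one sentence to Appendix C and section 17.2.1: analyses of the rate and duration of, and time to, cytogenetic response include only patients with Ph-positive metaphases at entry, while all randomised patients stay in the molecular, progression-free survival and overall survival analyses. Take entry as footnote 1 of section 11.2 defines it for patients who have already had imatinib. Report by arm how many patients are left out.

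Marrow cytogenetics at entry is already required, so no test is added. The subset is fixed by a baseline characteristic, so the comparison within it is still randomised. Evaluability should not depend on whether optional FISH happened to be done during follow-up: that is decided after randomisation, and the trial is open label.

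The cost is a slightly smaller denominator for a secondary endpoint: about 3 to 33 fewer of 330 patients at the assumed shares, with numbers that may differ a little between arms.

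Separately, the inclusion criterion and the criterion for progression from major cytogenetic response do not fit together for Ph-negative patients. Section 10 also uses that criterion for ending protocol treatment, so the investigators should reconcile these sections. No clinical rule is proposed here.
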